This study (Study 20180130) will provide the opportunity to investigate the long-term safety profile in paediatric patients with respect to known short-term toxicities of blinatumomab, eg, those related to the immune, neurologic, and HSCT-related events. The study will involve long-term follow-up of both chemotherapy- and blinatumomab-treated paediatric patients who then undergo alloHSCT. Patients who have undergone alloHSCT following treatment with either blinatumomab or standard of care (SOC) chemotherapy will be invited to participate in the 20180130 study.

Study 20180130 will provide the opportunity to investigate the long-term safety profile of blinatumomab, by providing 12 years of follow-up of patients treated with either blinatumomab or chemotherapy, followed by alloHSCT (follow-up commencing at transplantation). The study will investigate neuropsychomotor developmental impairment, endocrine impairment, neurological impairment, and immune system impairment.

- Research Question and Objective(s)
 - Primary Objective

(1) To estimate incidence of neuropsychomotor developmental impairment, endocrine impairment, neurological impairment, and immune system impairment (including auto-immune disorders and vaccine failure)

- Secondary Objectives
 - (1) To estimate the incidence of HSCT related adverse events (AEs)
 - (2) To estimate the incidence of subsequent relapse of leukemia including in the CNS
 - (3) To estimate the cumulative incidence of long-term AEs
 - (4) To estimate the incidence of secondary malignant formation
 - (5) To estimate overall survival
- Hypothesis Estimation
 - The study will compare blinatumomab therapy versus chemotherapy treatment

for the occurrence of neuropsychomotor developmental impairment, neurological impairment, endocrine impairment, and immune system impairment.

• Study Design/Type

This study is a prospective observational study.

• Study Population or Data Resource

Paediatric patients who have undergone alloHSCT following treatment with either blinatumomab or SOC chemotherapy will be invited to participate in the study.

• Summary of Patient Eligibility Criteria

Inclusion Criteria

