9.2.1 Study Period

Enrolment of patients into 20180130 will occur if they meet all eligibility criteria. All eligible patients or their caregivers/legal guardians will be approached to provide informed consent for participation. Once informed consent has been given, and all inclusion/exclusion criteria are met, the patient will be enrolled via interactive response technology (IRT) in the study and data collection will begin. The study will commence at the first data collection of the first site. Patients will be followed for a maximum of a 12-year period or up to the age of 25 years, death, withdrawal of consent, or loss to follow-up, whichever comes first. The study will end when 12 years of follow-up for the last patient (if the patient has not withdrawn consent, been lost to follow-up, or died before the end of the 12 years of follow-up) is completed. If the last patient enrolled on study dies or is lost to follow-up before the 12 years following alloHSCT, the remainder

of the patients on study will continue to be followed until all patients on study have reached 12 years following alloHSCT, until death, withdrawal of consent, or lost to follow-up, whichever occurs first.

Data will be entered into an eCRF and will encompass information abstracted from patient charts from routine clinical visits. Data abstraction will be performed approximately every 6 months (± 30 days) starting at enrolment. Additional data on neuropsychomotor development will be assessed through specific questionnaires (paper and/or electronic) which will be administered at pre-specified intervals starting at enrolment (approximately every 6 months [± 30 days] for patients up to 6 years old and approximately yearly [± 60 days] for patients from 6 years old).

The first day of follow-up (day 1) will be the date of successful completion of alloHSCT (following chemotherapy/ blinatumomab treatment).

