9.2.2 Selection and Number of Sites

Sites participating in Study 20120215 may be selected (planned in Europe, Israel, Australia, and Latin America) and further centers located in (but not limited to) Europe, Israel, Australia, Brazil, Canada, Mexico, United States, outside of Study 20120215 are planned to be included in this 20180130 study. The final number (and locations) of sites has not been confirmed.

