9.2.3 Patient Eligibility

9.2.3.1 Inclusion Criteria

Patients are eligible to be included in the study if they meet all of the following inclusion criteria.

- Paediatric B-cell precursor ALL patients with any indication world-wide that received blinatumomab or chemotherapy in routine clinical practice, followed by transplantation, or EU paediatric indications that may be authorized in the future. This means that paediatric patients which receive blinatumomab off-label in the EU or with a different indication in ex-EU regions may be included in the study.
- Patient's legally acceptable representative has provided informed consent when the patient is legally too young to provide informed consent and the patient has provided written assent based on local regulations and/or guidelines prior to any study-specific activities/procedures being initiated.

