9.2.3.2 Exclusion Criteria

NA

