9.7.2 Planned Method of Analysis

All analyses will sub-grouped by blinatumomab consolidation or chemotherapy consolidation group. Continuous variables will be summarized by mean, median, standard deviation, 25th percentile, 75th percentile, minimum and maximum. Categorical variables will be summarized by number and percentage. For categorical outcomes, 95% confidence intervals will also be presented where appropriate. For time-to-event endpoints, Kaplan-Meier (KM) curves and estimates (median, 1st and 3rd quartile) of the time-to-event endpoint with 95% confidence intervals will be calculated, if estimable. Tables will be presented for the total patient population (ie, those who meet the eligibility criteria). Pending adequate sample size is enrolled (≥50 patients per arm), comparison analysis between blinatumomab and chemotherapy groups will be conducted by logistic

or Cox regression models generating an odds ratio or hazard ratio with 95% CI confidence intervals.

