9.7.2.2.3 Analysis of the Primary and Secondary Endpoints

Patient incidence proportions (and 95% Cls) for each of the specified outcome events will be summarized. KM estimates for time to first onset of each specified event will be provided.

For the events of interest, events that occur after a relapse or secondary malignancy will be censored as it is unlikely that events that occur after relapsed and treatment for relapse could be considered related to initial chemotherapy or blinatumomab treatment for the prior disease occurrence.

A comparison between the blinatumomab versus chemotherapy group will be conducted at the final follow-up in the study pending adequate sample size is enrolled $(\geq 50 \text{ patients per arm})$ and the blinatumomab and SOC groups are comparable (eg. there is overlap between PS distributions across the two groups, or no critical differences that cannot be accounted/adjusted for). Prior to comparison being conducted, covariates listed in Section 9.3.2 will be evaluated for differences between the two groups. Any covariates that are not comparable between the two (Wald chi-square or t-test, p-value < 0.25), will be evaluated as a covariate for adjustment in the models. The primary and secondary endpoint of discrete events (eg, incidence endpoints) will be compared by a logistic regression which will generate an odds ratio and 95% confidence interval of the odds of developing an event. Endpoints that are time-to-event will be compared by a Cox regression model which will generate hazard ratio and 95% confidence interval for the risk of developing an event. Also, we will additionally conduct a propensity score weighting analysis based on the covariates collected for this study. An additional sensitivity analysis may be done to adjust for the drop-in effect of patients receiving anti-cancer medications during follow-up.

A literature review of published data at the time of the final study report will be performed for the relevant endpoints. If there is any relevant scientific data publicly available by the time when the study ends (> 12 years later), Amgen will provide a comparative analysis. If a sufficient number of patients are identified in publicly available database with information on relevant confounding factors, Amgen will conduct a direct comparative analysis, but descriptive analyses will be undertaken either way.

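### Patients who relapse or develop a second malignancy between transplant and consent can enrol but can supply no countable questionnaire-defined neuropsychomotor event, yet they stay in that endpoint's denominator and in the 50-per-arm gate

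*Protocol*

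**What the plan says.** Eligibility (Sections 9.2.3.1 and 9.2.3.2): the patient must have "received blinatumomab or chemotherapy in routine clinical practice, followed by transplantation", and consent must be in place. Exclusions are given as not applicable. Nothing requires freedom from relapse or second malignancy since the index transplant, and no maximum time from transplant to enrolment is set.

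Timing of the invitation (Abstract): "Patients who have undergone alloHSCT following treatment with either blinatumomab or standard of care (SOC) chemotherapy will be invited to participate". Section 9.2.2 adds that "Sites participating in Study 20120215 may be selected".

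Clock and assessments (Section 9.2.1): day 1 of follow-up is the transplant date, but the questionnaires are "administered at pre-specified intervals starting at enrolment". Section 9.3.1 defines neuropsychomotor impairment by questionnaire score: two or more standard deviations from the norm in the adverse direction, an age-equivalence rule for motor skills from age 10, and changes from the patient's own baseline.

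Analysis (Section 9.7.2.2.3): "events that occur after a relapse or secondary malignancy will be censored". Incidence proportions, Kaplan-Meier estimates, logistic regression for incidence endpoints and Cox regression for time-to-event endpoints are all planned.

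Denominator and gate (Section 9.7.2): "Tables will be presented for the total patient population (ie, those who meet the eligibility criteria"). The comparison of the two groups opens once at least 50 patients per arm are enrolled.

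**The concern.** Each of these rules is reasonable alone, but together they leave a gap. Eligibility and the gate count patients at consent. The questionnaires also start at consent. The censoring rule closes the countable period at relapse or second malignancy, which may come before consent. For such a patient the window in which a neuropsychomotor event could be both observed and counted is empty.

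Neuropsychomotor impairment is the first outcome named in the primary objective. If patients with an empty window stay in its denominator, the incidence is understated. In a safety study that is the unwelcome direction. The gate of 50 would also overstate how many patients per arm can inform the comparison on this endpoint.

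**Working it through.** **1. Is the window really empty?** Take a patient with transplant on day 1, relapse at time R and consent at time C, with R before C.
- Eligible: yes (9.2.3.1, 9.2.3.2).
- First questionnaire: at C (9.2.1).
- Events counted: only those before R (9.7.2.2.3).
- Questionnaire scores obtained before R: none.

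No score-defined event can be counted. For the three other primary outcomes the window from day 1 to R is not empty. They do not depend on the questionnaires, and Section 9.6 has chart data documented from primary diagnosis onward, so events between transplant and relapse still count.

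**2. The plan's own size.** Section 9.5 gives 52 / 0.35 = 148.6, rounded up to 149 per arm and 298 in total. This reproduces. That calculation assumes that 85% to 98% of patients have at least one event, which the section supports with haematological toxicity and immune complications. It was not built on the neuropsychomotor endpoint.

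**3. Size of the dilution.** Let f be the share of enrolled patients with relapse or second malignancy before the first questionnaire. The protocol gives no value, so f = 5%, 10% and 20% are assumptions. A true neuropsychomotor incidence of 20% is also assumed.
- Incidence as read, with all eligible patients in the denominator: 20% × (1 − f).
- Informative patients among 50 enrolled per arm: 50 × (1 − f).
- Enrolment needed for 50 informative patients: 50 / (1 − f), rounded up.

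| f | Incidence as read | Informative of 50 | Enrol per arm to have 50 |
|---|---|---|---|
| 5% | 19% | 47.5 | 53 |
| 10% | 18% | 45 | 56 |
| 20% | 16% | 40 | 63 |

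**4. Effect on the comparison.** With the same f in both arms, the risk difference is also multiplied by (1 − f). As an illustration, assume 30% versus 20% and f = 20%. These read as 24% versus 16%, so the difference falls from 10 to 8 points. The odds ratio falls from (0.30/0.70)/(0.20/0.80) = 1.71 to (0.24/0.76)/(0.16/0.84) = 1.66.

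**5. Scale against sampling error.** At 149 per arm and 20% incidence, the 95% half-width is about 1.96 × √(0.2 × 0.8/149) = 6.4 points. The dilution in step 3 is 1 to 4 points. It is smaller than this, but it is systematic and always downward.

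**The case against.** The strongest reply is that the protocol says these events are censored; it does not say that the patients are scored as unimpaired. A reader might infer that they count as unimpaired throughout, and the text does not support that. In Kaplan-Meier and Cox analyses they would be censored. The dilution arises in the incidence proportion and the logistic model, and only if the all-eligible denominator in 9.7.2 is applied to them. Section 9.7.2.2.1 mentions analysis sets, and a statistical analysis plan not shown here may define a narrower one. Even so, the only denominator and gate that the protocol states do include these patients.

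A reader might also infer that their data are useless for the whole primary objective, or that they hollow out the 149 per arm. Neither follows. Chart-based neurological, endocrine and immune events before relapse count, so these patients can still be cases on the endpoint used for sizing. Dividing by 0.35 already allows for 65% of entrants not being long-term survivors, and many patients who have relapsed would plausibly fall in that group.

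It can be said further that 9.6 lists developmental impairment among the abstracted data and that the questionnaires are described as additional. But 9.3.1 defines impairment by score, so a chart note would not meet the stated definition.

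Finally, the number affected is unknown. Section 7.1.2 reports about 50% second relapse within 2 years after high-risk first relapse, and it is tempting to turn that into an expected share. It is not stated as a post-transplant rate, any indication may enrol, and the protocol gives neither the gap from transplant to consent nor the proportion of relapsed patients who would consent. Nor does anything in the protocol show that the share would differ between arms.

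**Conclusion.** The point holds for the questionnaire-defined neuropsychomotor endpoint. As written, eligibility, questionnaire start and censoring combine so that some enrolled patients cannot have a countable event on it, while the stated denominator and the 50-per-arm gate include them. The size rests on an assumed share: at 5% to 20% of enrolled patients, a true 20% incidence reads 1 to 4 points low, and 2.5 to 10 of every 50 patients per arm do not inform the comparison. With a share near zero the effect vanishes. This is a modest, one-directional error that is cheap to prevent. It does not undermine the other three primary outcomes or the sample-size target.

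**What to change.** Keep these patients enrolled for relapse, second malignancy, survival and chart-based outcomes up to relapse. Then change Section 9.7.2.2.3 as follows:
- Restrict the neuropsychomotor at-risk set to patients free of relapse and second malignancy at the first questionnaire.
- In the time-to-event analysis of this endpoint, let patients enter at that questionnaire. Time since transplant with no questionnaire is then not counted as time at risk.
- Apply the 50-per-arm gate for the neuropsychomotor comparison to that set.
- Report by arm how many patients were removed and why.

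Do not add an exclusion criterion for relapse or second malignancy before consent. Those events and overall survival are secondary endpoints, with survival timed from transplant, so excluding on them would bias their estimates.

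The cost is a few sentences of text and a slightly smaller denominator and gate count for this one endpoint. If 5% to 20% of enrolled patients are affected, that gate would need 53 to 63 enrolled per arm rather than 50.

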9.2.4 Baseline Period

The baseline period will be considered as the time between initial diagnosis of ALL and the alloHSCT. Specific clinical and treatment characteristics will be collected at specific time points during baseline (eg, at diagnosis, prior to SOC/blinatumomab therapy, up to alloHSCT transplant, etc).

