9.3.2 Covariate Assessment

Baseline

- Recording of ALL-related diagnoses history both prior to and following blinatumomab/SOC chemotherapy
 - Disease status (prior to blinatumomab/SOC chemotherapy)
 - MRD status (following treatment; MRD positivity defined at a level $\ge 10^{-4}$ in PCR and/or flow quantification)
 - Relapse (following treatment)
 - Time point of relapse (time since primary diagnosis and time after completion of primary therapy)
 - Whether extramedullary relapse
 - Bone marrow status at relapse
 - Secondary malignancy (following treatment)
- Recording of ALL-related treatment history
 - Details of SOC-chemotherapy therapy
 - Specific therapy
 - Duration of therapy
 - Details of blinatumomab therapy
 - Number of blinatumomab cycles
 - Occurrence of further blinatumomab therapy following initial discontinuation
 - Duration of blinatumomab therapy
- Recording of alloHSCT status
 - Occurrence of alloHSCT
 - Interval between SOC-chemotherapy/blinatumomab and alloHSCT
- Clinically relevant events prior to initiation of therapy or after initiation of therapy and before alloHSCT (see definitions above)
 - Neurological event
 - Endocrine event (including evidence of growth delay)
 - o Immune event
 - Toxicity (gastrointestinal, hematologic, dermatology, cardiac, pulmonary, hepatic, renal, infection, skeletal, etc.: see definitions above)
- Other important clinical factors
 - o Comorbidity
 - Concomitant medication
 - Prenatal development
 - High-risk pregnancy
 - Delivery complications including hypoxia
 - o Gestational time at the delivery
 - APGAR score
 - o Gestational weight (intrauterine growth restriction [IUGR])
 - Psychomotor development impairment and psychiatric conditions recognised prior to the therapy
- Pregnancy and breastfeeding status after blinatumomab initiation

Follow-up

- Demographics and clinical characteristics including comorbidity
 - All treatments for ALL
 - Pregnancy and breastfeeding status

- Recording of further ALL-related treatment history
 - Details of SOC-chemotherapy therapy: specific therapy, and; duration of therapy
 - Details of blinatumomab therapy: number of cycles; occurrence of further blinatumomab therapy following initial discontinuation, and; duration of therapy
- Further HSCT
 - Occurrence of HSCT
 - o Interval between SOC-chemotherapy/blinatumomab and HSCT
 - Outcome of HSCT: early/late GvHD; infection; HSCT-related toxicity (see definitions above)

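### Covariates for the blinatumomab-versus-chemotherapy comparison are not limited to those fixed before the compared therapy, so the models may condition on its consequences

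*Protocol*

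**What the plan says.** Section 9.7.2.2.3 sets the covariate rule for the comparison, and the Data Analysis part of the abstract (Section 4) repeats it. There are two steps.

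- Regression: "Prior to comparison being conducted, covariates listed in Section 9.3.2 will be evaluated for differences between the two groups". Then: "Any covariates that are not comparable between the two (Wald chi-square or t-test, p-value < 0.25), will be evaluated as a covariate for adjustment".
- Weighting: "we will additionally conduct a propensity score weighting analysis based on the covariates collected for this study". No screen applies here.

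Section 9.3.2 is the source list. Its baseline part includes:

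- "Clinically relevant events prior to initiation of therapy or after initiation of therapy and before alloHSCT (see definitions above"), covering neurological, endocrine and immune events and organ toxicity;
- MRD status, relapse and secondary malignancy, each marked as following treatment;
- "Number of blinatumomab cycles", duration of blinatumomab, and pregnancy or breastfeeding status after blinatumomab initiation.

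Its follow-up part includes all ALL treatments, further HSCT and "Outcome of HSCT: early/late GvHD; infection; HSCT-related toxicity (see definitions above"). Demographics also stand under follow-up.

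Two other sections bear on timing. Section 9.2.4: "The baseline period will be considered as the time between initial diagnosis of ALL and the alloHSCT". Section 9.9 describes the adjusters as baseline characteristics of the two groups, to be entered in the models where they differ.

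**The concern.** The exposure compared is the therapy given before transplant (Sections 7.3 and 9.1). An adjustment set for its effect should hold variables settled before that therapy began. Events between the start of therapy and alloHSCT can be caused by it, and so can MRD status after it. They may lie on the path from blinatumomab to long-term impairment.

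That path is a reason for the study. The abstract frames the study around the long-term picture for known short-term toxicities. Section 7.2 says that neurologic events occur mostly at the beginning of treatment and that their impact, particularly in children under two, is unknown. A model that holds early neurologic events fixed sets aside the route by which they might lead to later impairment. In a post-authorisation safety study the resulting error could make harm look smaller than it is. It would give no warning, because the model fits normally.

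The p < 0.25 screen does not protect against this. It tends to select the variables that treatment itself has made different.

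**Working it through.** The protocol states no figure on this point, so none can be reproduced. The only protocol numbers used are the group sizes, 149 per arm (52/0.35 = 148.6, Section 9.5) and 50 per arm (the gate in Section 9.7.2.2.3), and one event rate from Section 7.1.3. All other rates are assumptions.

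**Step 1. Timing of the Section 9.3.2 items relative to the start of the compared therapy**

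| Item | Timing |
|---|---|
| Prenatal and delivery history, earlier psychomotor or psychiatric conditions, disease status before therapy, events before therapy | Before |
| Neurological, endocrine, immune and toxicity events between therapy start and alloHSCT | After |
| MRD status and secondary malignancy following treatment | After |
| Relapse following treatment | Unclear: the sub-items on time since diagnosis and since primary therapy could describe the relapse that led to index therapy |
| Blinatumomab cycles and duration | After, and in one arm only |
| Later ALL treatment, further HSCT and its outcomes | After alloHSCT |

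Section 9.2.4 places every row except the last inside baseline.

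**Step 2. Effect wholly through an early event (closed form)**

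P(impairment | arm) = pE × 0.50 + (1 − pE) × 0.15, where pE is the early-event rate and 50% and 15% are assumed impairment risks with and without the event. For blinatumomab pE = 13.8%, the neurologic figure among the most serious reactions in Section 7.1.3. The chemotherapy rates of 3% and 5%, and the 30% and 10% pair, are assumed.

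- 13.8% vs 3%: 0.1983 vs 0.1605, difference 3.8 points, OR 1.29.
- 13.8% vs 5%: 0.1983 vs 0.1675, difference 3.1 points, OR 1.23.
- 30% vs 10%: 0.255 vs 0.185, difference 7.0 points, OR 1.51.

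Given the event, the OR is 1.00 in each case, because no direct effect was assumed.

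**Step 3. With and without a direct effect (1,000 simulated studies per setting, 50 and 149 per arm)**

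Assumed: early event in 40% (blinatumomab) vs 15% (chemotherapy); OR 5 of the event on the outcome; log-odds −1 of the outcome with chemotherapy and no event, that is 26.9%, or 64.8% with the event. Check of the mediated case: 0.40 × 0.648 + 0.60 × 0.269 = 0.421 and 0.15 × 0.648 + 0.85 × 0.269 = 0.326, giving OR 1.50.

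| Direct OR | Event left out | Event in regression | Weighted on event |
|---|---|---|---|
| 1.0 | 1.49–1.50 | 0.97–0.99 | 0.99–1.00 |
| 1.5 | 2.14–2.16 | 1.50–1.52 | 1.43–1.45 |

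**Step 4. What the screen selects**

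This is the probability that a two-sided z-test of two proportions gives p < 0.25, with an event rate of 15% in the lower arm:

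| Difference | 149 per arm | 50 per arm |
|---|---|---|
| 10 points | 0.85 | 0.54 |
| 15 points | 0.98 | 0.74 |
| 25 points | 1.00 | 0.96 |

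For 13.8% vs 3% and 13.8% vs 5% it is 0.99 and 0.94 at 149 per arm, and 0.83 and 0.68 at 50 per arm.

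**Step 5. Cycle count**

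With cycle count set to 0 for chemotherapy (an assumed coding) and 149 per arm, a logistic propensity model separates completely. It did not converge; scores were below 1e-13 in one arm and above 0.999999 in the other. The outcome regression with arm and cycle count could still be fitted, but in that simulated data set the standard error of the arm effect rose from 0.24 to 0.43.

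**The case against.** The strongest defence is that the text commits to less than it seems to.

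- *Automatic adjustment.* A reader might infer that every Section 9.3.2 item enters the models. The documents do not support that for the regression: items must pass the screen and are then only evaluated. The final propensity list may also be left to an SAP. But the protocol names the source of both sets, and nothing in it keeps post-treatment variables out.
- *Baseline only.* Section 9.9 speaks of baseline characteristics, and Section 9.7.2.2.3 leaves later anti-cancer medication to a possible sensitivity analysis. Both point away from the follow-up list. They do not exclude the pre-transplant events, because Section 9.2.4 counts the treatment period as baseline.
- *Endpoint components as covariates.* A reader might infer that GvHD and infection after the index transplant would be adjusted for. In Section 9.3.2 those outcomes stand under further HSCT, so that reading is not supported.
- *Cycle count.* It has no value in the chemotherapy arm, and the protocol does not say to code it 0. An analyst would probably drop it. The mediators give no such visible signal.
- *Size.* The rates are not the protocol's, and the OR of 1.00 follows from assuming no direct effect. This stands: the figures show direction and mechanism and do not forecast the bias.
- *Reach.* The primary objective is to estimate incidence, and the comparison depends on enrolment and comparability. This also stands.

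**Conclusion.** The rule is badly fixed. Followed as written, it allows, and for weighting on its literal wording calls for, conditioning on consequences of the therapy being compared. This biases the arm comparison whenever such events affect later impairment. Steps 2 and 3 show the possible size, under assumed event rates and event-outcome associations.

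A reader might conclude that the comparison removes the whole treatment effect or cannot be fitted. Neither follows. Only the part running through the adjusted events is lost: with a direct OR of 1.5, adjustment still returned about 1.5. Complete separation concerns only a propensity model holding a blinatumomab-specific variable coded 0 for chemotherapy. Nor need the comparability gate fail, since overlap is one example there beside an alternative criterion.

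**What to change.** 1. In Section 9.7.2.2.3, the abstract and Section 9.9, limit the adjustment and propensity-score set for the main comparison to variables fixed before the first dose of index blinatumomab or SOC chemotherapy: age, sex and other demographics, disease status and relapse history before index therapy, prior treatment, comorbidity and events before therapy, and prenatal and developmental history. Name demographics explicitly; because Section 9.3.2 lists them under follow-up, a blanket bar on follow-up items would exclude them.
2. Exclude from the main models arm-specific variables, events and disease status arising after index therapy starts, and post-transplant follow-up variables. Keep them for descriptive, mediation or sensitivity analyses.
3. Split the Section 9.2.4 baseline into a period before index therapy and a period from index therapy to alloHSCT.
4. State in Section 9.3.2 whether relapse following treatment means relapse before or after index therapy.
5. Reconcile the abstract with Sections 9.2.4, 9.3.2, 9.7.2.2.3 and 9.9.

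The cost is mainly wording. Section 9.2.4 already plans collection before SOC or blinatumomab therapy. The eCRF must show whether each pre-transplant event came before or after therapy began, since Section 9.3.2 lists both under one item. The change should be made before the final comparison is run.
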